**5.4.2.2.6. St. George's Respiratory Questionnaire (SGRQ)**

The changes from baseline in total score of SGRQ and domain scores will be summarized descriptively at Weeks 24, 48, and 60. For the total score of SGRQ at Week 24, the difference in the change from baseline between the treatment groups will be provided using an analysis of covariance (ANCOVA) model. The baseline total score will be used as covariate in the analysis.

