### **6.3. Measures to Minimize Bias: Randomization and Blinding**

It is an open-label study; however, participants will be randomly assigned to 1 of 2 treatment groups based on a computer-generated randomization schedule prepared before the study. The randomization will be balanced by using randomly permuted blocks and will be stratified by country.

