**VERSION HISTORY****Table 1: SAP Version History Summary**

SAP Version	Approval Date	Change	Rationale
1	26 February 2021	Not Applicable	Initial release
2	25 April 2022	
 
Appendix 11 (Unblinding Plan), Appendix 12 (Agreement on the Unblinded Information Handling) and Appendix 13 (Running Log of Default Unblinders) were added.
 
The definition of culture reversion (relapse or reinfection) was added in Section 5.5.2.
 
Other changes were made to keep consistency with the protocol.
 
	
 
Detailed unblinding plan which was added in the protocol Amendment 6.
 
Clarified the definition of culture reversion.
 

3	24 May 2024	
 
Appendix 11 (Unblinding Plan) and Appendix 12 (Agreement on the Unblinded Information Handling) were updated.
 
Region and duration of previous therapy for MAC-LD were added in Appendix 3 (Demographics and Baseline Characteristics).
 
Other changes were made to keep consistency with the protocol and correct errors.
 
	
 
Clarified unblinders and scope of blinding.
 
Reflected study design changes from protocol Amendment 7 to Amendment 8.
 

4	31 January 2025	
 
Definition of analysis phase was modified to include data after switching to individualized treatment regimen in the investigational phase.
 
Visit window for optional cohort was modified to use the start date of optional treatment as baseline.
 
Region (Japan, non-Japan) was added as a stratification factor in statistical tests.
 
The supplementary estimand considering for treatment non-compliers was deleted.
 
Other changes were made for clarification, error correction or consistency with other study documents.
 
	
 
Investigational treatments are included in individualized treatment regimen.
 
Variable washout period before start of optional treatment is considered.
 
Based on the advice from PMDA.
 
All subjects are compliers defined as 80% or more compliance.
 

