##### **5.3.2.1. Main Estimator of the Primary Estimand**

#### **Assumptions**

- Missing not at random: missing data due to deaths, treatment discontinuation and treatment regimen changes will be treated as nonconversion.

- No prognostic factors for the proportion of converters.

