### Analysis Methods

Cochran-Mantel-Haenszel test stratified by region (Japan, non-Japan) at the 5% 2-sided significance level will be used to compare sputum culture conversion rate in MGIT at Week 24. The proportion of the participants with sputum culture conversion at Week 24 will be summarized as randomized and the stratum adjusted treatment difference with 2-sided 95% CI will also be presented.

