## Analysis Methods

Cochran-Mantel-Haenszel test stratified by the type of MAC (*M. avium* only or other) at the 5% 2-sided significance level will be used to compare sputum culture conversion rate in MGIT at Week 24. The proportion of the participants with sputum culture conversion at Week 24 will be summarized as randomized and the stratum adjusted treatment difference with 2-sided 95% CI will also be presented.

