## Analysis Methods

The Cochran-Mantel-Haenszel test stratified by region (at the 5% 2-sided significance level) will be used to compare sputum culture conversion rate in MGIT at Week 24. The proportion of the subjects with sputum culture conversion at Week 24 will be summarized as randomized and the treatment difference with 2-sided 95% CI will also be presented.

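### The Week 24 SGRQ ANCOVA and the MAC-type sensitivity test leave out region, which every other between-arm efficacy test includes; the cost is small and conservative, but the sensitivity test then changes two things at once

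*SAP*

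**What the plan says.** **Design.** Protocol 6.3: "The randomization will be balanced by using randomly permuted blocks and will be stratified by country". The countries are Japan, South Korea and Taiwan.

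**Region in the analyses.** The SAP version history lists, for version 4, "Region (Japan, non-Japan) was added as a stratification factor in statistical tests". The reason given is PMDA advice, and no exception is named. The primary analysis (SAP 5.3.2.1) follows suit: "Cochran-Mantel-Haenszel test stratified by region (Japan, non-Japan) at the 5% 2-sided significance level will be used". Region also appears in:
- the supplementary estimand (5.3.3.1);
- agar conversion at Week 24 (5.4.2.2.1);
- the Week 60 comparison of MGIT conversion (5.4.2.2.2);
- the culture-negativity CMH test and generalized linear model (5.4.2.2.3);
- the log-rank test (5.4.2.2.4).

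**The two exceptions.**
- SAP 5.4.2.2.6, on the Week 24 SGRQ ANCOVA: "The baseline total score will be used as covariate in the analysis". No other covariate is named, and protocol 9.4.4 names none.
- SAP 5.3.2.2, the sensitivity estimator of the primary estimand: "Cochran-Mantel-Haenszel test stratified by the type of MAC", in two levels (*M. avium* only, or other). Region is not mentioned. The data included and the missing-data rules are those of the main estimator.

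SAP Appendix 2, on changes to protocol-planned analyses, does not comment on either omission.

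**Interval wording.** SAP 5.3.2.1 and 5.3.2.2 call for a stratum-adjusted difference. SAP 5.3.3.1 specifies a region-stratified test, but the result is to be "summarized as randomized and the treatment difference with 2-sided 95% CI will also be presented". SAP 5.4.2.2.1 and 5.4.2.2.3 are worded in the same way.

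**The concern.** When arms are balanced within strata and the analysis ignores the strata, any between-stratum variation in outcome stays in the residual. The estimated standard error is then larger than the true one. The analysis remains valid but is conservative, and some precision is thrown away. Protocol Table 2 shows that background drug doses differ between Japan and the other two countries, so a regional difference in outcome is conceivable.

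The second issue needs no effect size. A sensitivity analysis should change one assumption so that its result can be read. SAP 5.3.2.2 is built to test one: the main estimator assumes "No prognostic factors for the proportion of converters", and the sensitivity estimator allows MAC type to be prognostic. As written, it also removes region. If its result departs from the primary, the reader cannot say which change was responsible.

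**Working it through.** **1. The plan's own figure.** Inputs from SAP 3: 62 per arm, 10% v 30%, two-sided 5%, chi-square test. With mean rate 0.20:

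power = Φ[(0.20·√62 − 1.96·√(2·0.20·0.80)) / √(0.10·0.90 + 0.30·0.70)] = 0.803.

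This reproduces the stated power of about 80%, and 62 per arm is the matching sample size without continuity correction.

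**2. SGRQ ANCOVA.** Let s be the share of participants outside Japan and d the regional difference in SGRQ change, in within-region residual SDs after baseline adjustment. The documents give neither, so both are assumed. With arms balanced within region,

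SE without region / SE with region = √(1 + s(1−s)d²).

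| d | s = 0.1 | s = 0.2 | s = 0.3 | s = 0.5 |
|---|---|---|---|---|
| 0 | 1.000 | 1.000 | 1.000 | 1.000 |
| 0.25 | 1.003 | 1.005 | 1.007 | 1.008 |
| 0.5 | 1.011 | 1.020 | 1.026 | 1.031 |
| 0.8 | 1.028 | 1.050 | 1.065 | 1.077 |

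The largest entry is √(1 + 0.25·0.64) = √1.16 = 1.077.

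Only the estimated standard error grows. The treatment estimate itself is protected by the within-region balance. A contrast with 80% power when region is modelled has a standardised effect of 1.960 + 0.842 = 2.802. Without region it must exceed 1.960 × ratio on the true scale:
- d = 0.5, s = 0.5: Φ(2.802 − 1.960·1.0308) = Φ(0.781) = 78.3%.
- d = 0.8, s = 0.5: Φ(2.802 − 1.960·1.0770) = Φ(0.691) = 75.5%, or about 76%.

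At d = 0.5 the real two-sided error rate of a nominal 5% test is 4.3-4.8% over these shares.

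**3. Sensitivity test of the primary endpoint.** Simulated trials: 124 participants, arms balanced within region, overall rates 10% v 30%, 5,000 runs per scenario. Species was assumed independent of region and not prognostic, with 40% in the second category. In the gap scenarios, rates outside Japan are 10 points lower on control and 20 points lower on BDQ.

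| Scenario | Region | Species only | Region × species |
|---|---|---|---|
| No regional gap, s = 0.2 | 81.4% | 81.5% | 81.0% |
| Gap, s = 0.2 | 81.5% | 80.6% | 81.2% |
| Gap, s = 0.3 | 82.2% | 81.1% | 81.5% |

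Dropping region costs 81.5 − 80.6 = 0.9 points at s = 0.2 and 82.2 − 81.1 = 1.1 points at s = 0.3. With no gap the three tests are indistinguishable: the Monte Carlo error of each figure is √(0.81·0.19/5000) = 0.6 points. In a deliberately extreme null case (15% in Japan, 45% elsewhere, s = 0.3), the error rate was 4.8% with region, 3.5% with species only and 5.0% with both.

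**4. One change or two.** Set beside SAP 5.3.2.1, section 5.3.2.2 keeps the data set, missing-data rules, test family and significance level. It adds MAC type and removes region. That is two changes, while its stated assumptions motivate only the first.

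**The case against.** **No evidence that region is prognostic.** Protocol 2.1 says that dose differences among countries are not a major driver of efficacy and that no major regional difference in outcome is expected. The main estimator assumes no prognostic factors at all. This stands. A reader might infer that the intervals from these two analyses are too wide as a matter of course. The documents do not support that, and the range must include zero.

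**Power matters little for SGRQ.** SAP 5.4.1 defines no key confirmatory secondary endpoints, and SAP 5.4.2 lists SGRQ as supportive. SAP 5.4.2.2.6 provides a difference and states no significance level, so the version 4 note about tests need not cover it. This stands, and it limits the severity.

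**Region is not the randomisation stratum.** The stratum is country; Japan/non-Japan is a coarsening that the primary test also uses. So no analysis conditions on the exact stratum, and these two cannot be singled out for that. The inconsistency is with the SAP's own use of region.

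**Subgroup results will help.** SAP 5.3.4 gives treatment differences by region and by MAC species. They show how the effect varies, but they do not replace a sensitivity test that changes one assumption.

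**The interval wording is only ambiguous.** A reader might infer that unadjusted intervals are planned beside stratified tests. The sections do not say so, and even SAP 5.3.2.1 names no interval method. What remains is a drafting point.

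**Conclusion.** The omission is real and unexplained, and its consequences are minor. Both analyses are conservative if region is prognostic and lose nothing if it is not. For SGRQ, the standard error inflation is 0% with no regional difference, about 1-3% at 0.5 SD, and 7.7% at 0.8 SD with half the participants outside Japan. In that last case an 80%-power contrast falls to about 76%. A reader might instead shrink the standardised effect by 1.077 and get Φ(2.802/1.077 − 1.960) = 74%. That treats the true sampling error as inflated, which within-region balance prevents. The sensitivity test loses about 1 point of power under the assumed gaps.

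The better reason to act is interpretability: as specified, the sensitivity test cannot isolate the effect of allowing for MAC type. These sizes rest on assumed regional shares and differences. The primary test is unaffected.

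**What to change.** - **SAP 5.4.2.2.6:** fit the ANCOVA with treatment, baseline total score and region (or country). Region costs one degree of freedom.
- **SAP 5.3.2.2:** stratify the CMH test by region × MAC type (*M. avium* only or other). This makes four strata from 124 participants with an assumed 10% control rate, so check for sparse cells and state in advance how they will be handled. If region was dropped on purpose, say why.
- **SAP 5.3.3.1, 5.4.2.2.1 and 5.4.2.2.3:** as a minor alignment, describe the difference as stratum-adjusted, as in 5.3.2.1.

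Only SAP text changes. Region is already collected (SAP Appendix 3) and used in the primary test.

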**5.4.2.2.7. Lung function parameters**

The change from baseline of each lung function parameter will be descriptively summarized by visit.

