- q. In case of recurrence (relapse/reinfection) or in case of acquired resistance (at least 4-fold increased MIC) to BDQ is indicated by DST result, baseline and postbaseline isolates will be identified using WGS or VNTR if necessary. If more than 1 postbaseline positive culture (isolate) showing resistant is available the last culture positive sample will be tested for VNTR and/or WGS in addition to the baseline culture positive sample.
- r. Lung function test on Day 1 will be acceptable within 1 week prior to Day 1.
- s. Chest CT scans taken within 6 months prior to screening are acceptable.
- t. Single sparse blood samples will be collected for measurement of plasma concentrations of BDQ (and M2 [optional]). These samples can be taken at any time after intake of BDQ on the day, but the date and time of the second to last and the last administration of BDQ and CAM, respectively, and the date and time of blood draw must be recorded.
- u. Two blood samples will be drawn: one just before intake of BDQ or first intake of CAM in the visit, and the second sample between 2 to 4 hours after the intake. The date and time of the last study drug administrations of BDQ and CAM, respectively, prior to the first PK samples and the date and time of the study drug administrations immediately after the first PK samples must be recorded. The date and time of the blood draw must be recorded.
- v. Extra visits will be required for participants meeting certain grading thresholds for changes in QTcF. All ECGs will be performed in triplicate (3 ECGs within 5 minutes) and must be of good quality (stable baseline, free of interference and artefact). The ECG machine dedicated for this study must be used. All tracings will be transmitted for blinded central analysis. ECG at 2-4 hours post-dose of BDQ and CAM will be obtained at Week 2, Week 12, Week 24 and Week 48. ECG at pre-dose of BDQ and CAM will be obtained at Day 1, Week 4, Week 6, Week 8, Week 16 and Week 32. Those ECG should be performed within 20 minutes prior to PK blood sampling at every time point whenever possible. ECG will be performed before blood sampling at the other visit where time points of ECG measurement are not specified.

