### 9.4.1. General Considerations

All efficacy and safety data will be summarized by treatment groups (Groups A and B). For the Group B, data from optional cohort will be analyzed separately.

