
 
Clinical assessment: To evaluate the efficacy of BDQ compared with rifamycin when administered as part of a treatment regimen with CAM and EB in adult participants with treatment-refractory MAC-LD.
 
	
 
Change from baseline in patient-reported health status on total score of SGRQ at Weeks 48 and 60.
 
Change from baseline in lung function parameters at Weeks 24, 48, and 60.
 
Percentage of participants who undergo a change in their MAC-LD treatment regimen by Week 24, by Week 48 (Group A) and by Week 60 (Group B).
 

 
Microbiological assessment: To evaluate the efficacy of BDQ compared with rifamycin when administered as part of a treatment regimen with CAM and EB in adult participants with treatment-refractory MAC-LD at Week 60.
 
	
 
Percentage of participants with sputum culture conversion (defined as 3 consecutive negative sputum cultures taken at least 25 days apart) in MGIT and 7H10 or 7H11 agar media at Week 60.
 

 
To evaluate the safety and tolerability of BDQ compared with rifamycin when administered as part of a treatment regimen with CAM and EB in adult participants with treatment-refractory MAC-LD.
 
	
 
Safety and tolerability based on assessment of AEs, clinical laboratory assessments, 12-lead ECG, vital signs, physical examination, visual examination, and audiology up to Week 60.
 

 
To evaluate the PK of BDQ (and metabolite M2), and CAM (and metabolite 14-OH-CAM [optional]).
 
	
 
PK exposures of BDQ (and metabolite M2 [optional]) at Day 1, Weeks 2, 8, 12, 24, and 48, and CAM (and metabolite 14-OH-CAM [optional]) at Day 1, Weeks 2, 8, 12, and 24.
 

Exploratory	

 
Clinical assessment: To evaluate the efficacy of BDQ compared with rifamycin when administered as part of a treatment regimen with CAM and EB in adult participants with treatment refractory MAC - LD assessed by QOL-B NTM module.
 
	
 
Change from baseline in patient reported health status on score of QOL-B NTM module at Weeks 24, 48, and 60.
 

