### **Lung function parameters**

The lung function parameters including forced expiratory volume in one second, forced vital capacity, inspiratory capacity, functional residual capacity, and total lung capacity, will be assessed.

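### Lung function has a bedaquiline-versus-rifamycin objective, but the SAP pre-specifies only descriptive summaries; a Week 24 baseline-adjusted difference with a confidence interval would be a cheap improvement

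*SAP*

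**What the plan says.** SAP 1.1 and Protocol 3 list the endpoint "Change from baseline in lung function parameters at Weeks 24, 48, and 60" among the secondary endpoints. The objective in that row begins: "To evaluate the efficacy of BDQ compared with rifamycin when administered as part of a treatment regimen with CAM and EB in adult participants". The same row holds SGRQ total score at Weeks 48 and 60 and the percentage of participants who change regimen. Protocol 4.1 names lung function, with culture conversion and SGRQ, as a key efficacy assessment.

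SAP 5.4.2.1 names five measures: "The lung function parameters including forced expiratory volume in one second, forced vital capacity, inspiratory capacity, functional residual capacity, and total lung capacity". SAP 5.4.2.2.7 gives the method in one sentence: "The change from baseline of each lung function parameter will be descriptively summarized by visit". Protocol 9.4.4 contains no lung function analysis. That the summaries are split by arm comes from the general rule in Protocol 9.4.1, not from the SAP sentence.

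For SGRQ total score at Week 24, SAP 5.4.2.2.6 says that "the difference in the change from baseline between the treatment groups will be provided using an analysis of covariance (ANCOVA) model", and adds: "The baseline total score will be used as covariate in the analysis". A baseline lung function value is collected; the footnotes to the Schedule of Activities say: "Lung function test on Day 1 will be acceptable within 1 week prior to Day 1". SAP 5.4.1 defines no key confirmatory secondary endpoints, and 5.4.2 labels the secondary endpoints supportive.

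**The concern.** The objective asks how the two regimens compare, and the planned output does not give that comparison with its uncertainty. Of the three key efficacy assessments named in Protocol 4.1, culture conversion gets a stratified test with a difference and interval, SGRQ gets an adjusted difference at Week 24, and lung function gets neither.

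This has some weight here. Protocol 4.2 says that markers predicting clinical response in this disease are not established, and the primary endpoint is microbiological. Support from clinical measures therefore matters to how the trial is read. The trial is open-label, and the other clinical secondary endpoints are a questionnaire and regimen changes made at the investigator's discretion; lung function is the instrument-measured one. If no comparison is pre-specified, any difference quoted later, and the choice of parameter to quote, will be post hoc.

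**Working it through.** **Step 1: set the endpoints side by side.**

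| Item | SGRQ total score, Week 24 | Lung function, Week 24 |
|---|---|---|
| Objective worded as bedaquiline versus rifamycin | Yes, in its own row tied to Week 24 | Yes, in a later row with no timepoint in the objective |
| Baseline collected | Yes | Yes |
| Pre-specified between-arm difference | Yes, ANCOVA | No |
| Baseline covariate | Yes | No |
| Missing-data rule | Scoring manual, for partly missing scores | None |

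**Step 2: confirm the sample size used below.** Protocol 9.2 and SAP 3 give 62 per arm for 10% versus 30% conversion at two-sided 5%. With the usual uncorrected formula and pooled proportion 0.20:

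n = [1.96 × √(2 × 0.20 × 0.80) + 0.842 × √(0.10 × 0.90 + 0.30 × 0.70)]² / 0.20² = (1.109 + 0.461)² / 0.04 ≈ 61.6, so 62 per arm. Power at 62 is 80.3%, against a stated value of about 80%. The figure reproduces. It concerns the primary endpoint only; no figure for lung function is stated.

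**Step 3: what precision a Week 24 difference would have.** The documents give no SD, correlation or dropout rate for lung function. I assume an SD of FEV1 change of 0.15 to 0.30 L. The unadjusted half-width is 1.96 × SD × √(2/n).

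- n = 62, SD 0.15 L: 1.96 × 0.15 × √(2/62) = 0.053 L
- n = 62, SD 0.30 L: 1.96 × 0.30 × √(2/62) = 0.106 L
- n = 40 (an assumed shortfall from missing tests), SD 0.15 L: 1.96 × 0.15 × √(2/40) = 0.066 L
- n = 40, SD 0.30 L: 1.96 × 0.30 × √(2/40) = 0.131 L

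**Step 4: what baseline adjustment adds.** With equal variances at the two visits and baseline-to-follow-up correlation ρ, the ANCOVA variance relative to the change-score variance is (1 − ρ²) / [2(1 − ρ)] = (1 + ρ)/2.

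| Assumed ρ | Variance ratio | Equivalent gain in participants (1/ratio − 1) |
|---|---|---|
| 0.5 | 0.75 | 33% |
| 0.7 | 0.85 | 18% |
| 0.9 | 0.95 | 5% |

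At high ρ the precision gain is small. Most of the benefit is in fixing the estimate, the interval and the parameter in advance.

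**Step 5: why Week 24.** Under Protocol 4.1, Group B non-converters may move to bedaquiline after the Week 24 assessment, and Group A non-converters leave the study at Week 48. Week 24 is the last planned lung function visit before those departures affect the randomised comparison.

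**The case against.** The best defence is that the SAP follows a visible hierarchy. SGRQ at Week 24 has its own objective row and gets a model. In the later row, SGRQ at Weeks 48 and 60, lung function and regimen change all have no between-arm model. Time to positivity is also purely descriptive. The comparative wording appears in nearly every objective, including safety, which SAP 5.6 declares free of inferential comparison. Protocol 9.4.4 promises no lung function comparison, so the SAP has dropped nothing. All of this stands, and it is why the point is minor.

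Stronger readings are tempting, but the documents do not support them:

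- A reader might infer that the trial will be unable to say whether lung function differs between regimens. Protocol 9.4.1 has efficacy data summarised by group. If those summaries give n, mean and SD, a crude difference and interval follow.
- A reader might infer that the baseline test was collected for ANCOVA and the model then forgotten. No section says so. Day 1 values are needed simply because the endpoint is change from baseline.
- A reader might infer that raw change scores would mislead. Under randomisation the unadjusted difference is unbiased; adjustment gains precision and handles chance imbalance.
- A reader might infer that SGRQ and lung function have identical standing, or that a questionnaire is the only other clinical secondary endpoint. SGRQ at Week 24 has a separate row, and regimen change is also listed.

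A practical objection also stands: the COVID-19 Appendix tolerates missed or off-date lung function tests, so fewer than 62 per arm may be evaluable.

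**Conclusion.** The point holds as a low-severity improvement. A supportive secondary endpoint with a comparative objective, named among the key efficacy assessments, has no pre-specified baseline-adjusted difference or confidence interval. The plan is permissible as written. The primary analysis, alpha and sample size are unaffected.

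The size is modest. The missing result is a Week 24 interval with a half-width of roughly 0.05 to 0.11 L for FEV1 before adjustment. That rests on assumed SDs and on all 62 per arm being evaluable, and it says nothing about the other four parameters. Baseline adjustment would cut the variance by 5% to 25% for assumed correlations of 0.9 down to 0.5.

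**What to change.** Add to SAP 5.4.2.2.7: 'At Week 24, the between-group difference in change from baseline, with its 95% CI, will be estimated for FEV1 (lead parameter) and for each other lung function parameter by ANCOVA with treatment, baseline value and region (Japan, non-Japan). The analysis includes ITT participants with a Week 24 value and uses all observed data regardless of regimen change before Week 24 (treatment policy). These intervals are supportive and carry no significance claim. Weeks 48 and 60 remain descriptive.'

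The treatment-policy rule matches the handling of regimen change in SAP 5.3.3. Region is not in the SGRQ ANCOVA as written; including it follows SAP version 4, which added region to the statistical tests. The documents rank no parameter, so FEV1 as lead is a proposal. What matters is that one is named before the Week 24 results are examined. The number with a Week 24 value should be reported by arm, because the analysis relies on observed values.

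The cost is one model per parameter on data already collected. The downside is up to five intervals without multiplicity adjustment, which the supportive label and the lead parameter keep in proportion.
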